Protocol Summary, Objectives, Study Calendar, Statistical and Data Management Considerations	Reporting the outcomes of late toxicity, breast cosmesis and local control at 2-3 years as well as at 5 years	To assess late toxicity, breast cosmesis and local control at 2-3 years, as well as at 5 years, because early results can provide valuable insights into the effectiveness and tolerability of treatments.
Patient Eligibility	Adding to inclusion criteria: women with previous contralateral breast cancer	A history of contralateral breast cancer does not compromise the radiotherapy treatment plan or the outcomes being assessed in this study.
Study Calendar	Removing KPS and Body weight	These data are redundant and not relevant for the study purpose
ECL	Adding to inclusion criteria: women with previous contralateral breast cancer	To reflect the change proposed in the section “Patient Eligibility”
No changes to the informed consent		

Summary of changes for Protocol version 5.0 dated 05JUL2023

Section(s)	Changes	Rationale
Cover page	Updating cover to reflect only the PI and the Co-PIs	To reduce multiple amendments that result due to change of personnel we will only have PI and the Co-PI information on the cover page.
No changes to the informed consent		

Summary of changes for Protocol version 4.0 dated 21OCT2022

Section(s)	Changes	Rationale
------------	---------	-----------

Adding personnel from Network sites	Adding personnel: NYP-Queens: [name], [name], [name], [name], [name], [name]. NYP-BMH: [name], [name] NYP-WCM – [name] and [name] (to IRB application. Note that [name] was already approved before. Removing [name], [name] and [name] from the study.	Adding and removing Personnel.
13.1 Reporting Adverse events	1. Clarifying that CTCAE version 5.0 will be used for this study. 2. Clarifying the DSMB will be reviewing Grade 3 and above events including SAEs. 3. Adding AE and SAE definitions.	Based on the DSMB memo issued on 24MAY2022.
Informed Consent changes		
Adding Key information section	Adding Key information section.	IRB requested changes.

Summary of changes for Protocol version 3.0 dated 09JAN2021.

Section(s)	Changes	Rationale
Adding Network sites	Adding NYP-BMH, NYP-Q as addition sites for patient enrollments	Adding sites.
Adding network sites	Adding NYP-BMH, NYP-Q as addition sites for patient enrollments	Adding sites

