where α / β is a tissue dependent parameter, arising from the radiobiological linear - quadratic cell survival model.

From the randomized prospective trials, there is an estimate that breast cancer may have an alpha/beta for tumor control of 4.6 and normal breast tissue an alpha beta ratio of 3.4 [6]. The relative closeness in alpha/beta ratios of tumor and normal tissue would support a rationale for hypo-fractionation [20-23]. Based on the formula above, Table 1 includes the calculation of BEDs (biologically equivalent doses) between the 2 arms. The breast cavity is predicted to have an alfa/beta value between 3-4.

Based on Table 1 a regimen of 42 Gy in 10 fraction to the boost is comparable to 48 Gy in 15 fractions. The latter regimen has been proven to both be effective (local recurrence rate <5% at 5 years) and to be associated with excellent cosmetic results (16), justifying our choice for a biologically equivalent regimen) in the experimental arm comparable to standard arm (see α/β values in Table 1, in bold).

In view of the fact that most recurrences tend to occur at the original tumor bed and that other studies have shown efficacy of lower doses of adjuvant radiation to the rest of the breast (4-8), we elect to test a dose of 32 Gy in 10 fractions. Maintaining a relative low dose to the rest of the breast tissue, which is a much lower risk of local recurrence than the area of the tumor cavity, will reflect on very low risk of fibrosis and will enhance the likelihood of optimal breast symmetry and cosmesis.

TABLE 1

Alfa/Beta (Gy)	2 Gy x 23	2.7 Gy x 15	3.2 Gy x 15*	3.2 Gy x 10	4.2 Gy x 10*
2	46	47	62.4	41.6	65.1
3	46	46.1	59.5	39.68	60.48
4	46	45.2	57.6	38.4	57.34
10	46	42.8	52.8	35.2	49.7

- Boost Dose delivered at tumor bed

3 Staging Criteria

TNM Stage 0 (Tis N0 M0), Stage I-II, T1-2 N0 M0, newly diagnosed breast cancer patients.

4 Patient Eligibility

Inclusion criteria:

1. Women status post segmental mastectomy
2. If unilateral, pT1-2 breast cancer excised with negative margins
3. If bilateral, pT1-2 breast cancer excised with negative margins AND/OR pTis excised with negative margins.
4. Clinically N0 or pN0 or sentinel node negative
5. Ductal carcinoma in situ DCIS with negative margins (no DCIS on inked margins).
6. Women with previous contralateral breast cancer.

Exclusion criteria:

1. Previous radiation therapy to the ipsilateral breast.
2. 90 days from last surgery, unless s/p adjuvant chemotherapy

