3. 60 days from last chemotherapy
4. Male breast cancer

5 Descriptive Factors/Stratification/Randomization Scheme

This is a prospective, randomized study. No stratification is planned. The study schema describes the study design.

5.1 Study Schema /Table 2

Eligibility	Stage 0 or Stage I-II breast cancer s/p segmental mastectomy.	
Day 0	Informed consent and randomization CT planning for determination of tumor bed on the prone position	
Days 1-15 (start within 90 days from last breast surgery)	Weekly IGRT, IMRT or Conformal breast irradiation, randomly assigned to: 15 fractions whole breast radiotherapy with concomitant boost (arm 1) or 10 fractions whole breast radiotherapy with concomitant boost (arm 2)	
Note: Patients with bilateral breast cancer will be randomized to receive the same dose and fractionation to both breasts		

6 Treatment plan

6.1.1 The women in this study will be randomly assigned to receive either 10 or 15 radiation fractions. The study design permits to test non inferiority of the 2 weeks versus 3 weeks regimen in terms of acute toxicity, fibrosis, breast cosmetic results and local control at 2-3 years and at 5 years follow up.

6.1.2 The informed consent process is as follows. The principal investigator explains all elements of the protocol to the patients and answers any and all questions. Clinical procedures are performed by the principal investigator. The research nurse will obtain blood sample by venipuncture. The consent process takes place in the Department of Radiation Oncology at Weill Cornell Medical Center. The consent form process is concluded when the patient, principal investigator and the witness all have signed the consent form. The witness is a present adult able to verify that the patient was given the proper information needed to make an informed decision to participate in the clinical study. year 1

6.1.3 Once the process of randomization is concluded, patients will be informed of the schedule based on the assigned one of the 2 arms.

6.1.4 Simulation and treatment will be started within 90 days from surgery, in order to maximize the chances of optimal lumpectomy cavity visualization on the planning and cone beam CT scans.

6.1.5 Our routine follow up is once a year after completion of radiation therapy. For the purpose of protocol significance (for assessment of fibrosis), we will require at least one follow up visit to our department, after years 2. (See 11.1 Study calendar).

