8.1 Cosmetic results assessment

Breast cosmesis will be assessed using the Breast Cancer Treatment Outcome Scale (BCTOS) patient self-reports before treatment (baseline), at the end of RT, at 1-month follow up visit and at 2-year follow up visit. This brief self-report instrument has high reliability and validity and has been used in a variety of previous studies on recovery from breast cancer treatment. [25]. The BCTOS also will be used as a primary measure to assess breast-related symptoms and treatment effects. The receipt of the survey will be recorded by the research nurses assigned to the study, but completion is not mandatory. Quality of life surveys will be sent to the patients’ personal email address at the baseline, at the end of RT, at 1-month follow up visit and at 2-year follow up visit. Completed responses will be sent directly to our REDCAP database. The quality of life survey completion is optional.

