Time point for this questionnaire (Do not mark in this box.)

- Baseline (after consent, before randomization)

Last week of radiation therapy

45-60 days after starting radiotherapy

Two years after adjuvant radiation therapy

This form is being filled out: (Mark one.)

 By participant in doctor's office	 By clinical staff, on phone with participant
 By participant not in doctor's office	 Other

*Record the participant's study ID on each of the remaining pages
before giving the questionnaire to the participant.*

Patient Study ID

Date this questionnaire is completed:
Month Day Year

(For example, if you were completing the questionnaire on September 8, 2004, you would write 09 08 2004 in the boxes.)

Thank you for completing this questionnaire.

We are interested in your evaluation of your physical appearance and functioning since you have been treated for breast cancer. Please rate the following items on this four-point scale, according to your evaluation at this point in time.

	Difference between treated and untreated breast and area			
	None	Slight	Moderate	Large
1 Breast size	1	2	3	4
2 Breast texture (hardening)	1	2	3	4
3 Arm heaviness	1	2	3	4
4 Nipple appearance	1	2	3	4
5 Shoulder movement	1	2	3	4
6 Arm movement	1	2	3	4
7 Breast pain	1	2	3	4
8 Ability to lift objects	1	2	3	4
9 Fit of shirt sleeve	1	2	3	4
10 Breast tenderness	1	2	3	4
11 Shoulder stiffness	1	2	3	4
12 Breast shape	1	2	3	4
13 Breast elevation (how high the breast is)	1	2	3	4
14 Scar tissue	1	2	3	4
15 Shoulder pain	1	2	3	4
16 Arm pain	1	2	3	4
17 Arm swelling	1	2	3	4
18 Breast swelling	1	2	3	4
19 Arm stiffness	1	2	3	4
20 Fit of bra	1	2	3	4
21 Breast sensitivity	1	2	3	4
22 Fit of clothing	1	2	3	4

BCTOS

Patient Study ID

--	--	--	--	--	--	--	--	--	--

We are interested in your personal reactions to the surgery you have received for your breast cancer. Please answer the following questions by circling one (1) number. Please note that the response options are labeled at the end-points only. However, you can and should use all of the points on the scale as appropriate to best convey your response.

1. To what extent has your surgery **disrupted** your normal daily activities?

0	1	2	3	4	5	6	7	8	9	10
Not at all					A lot					

2. To what extent has your surgery **disrupted** your normal recreational activities?

0	1	2	3	4	5	6	7	8	9	10
Not at all					A lot					

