1	EXCELLENT: when compared to the untreated breast or the original appearance of the breast, there is minimal or no difference in the size or shape of the treated breast. The way the breast feels (its texture) is the same or slightly different. There may be thickening, scar tissue or fluid accumulation within the breast, but not enough to change the appearance.
2	GOOD: there is a slight difference in the size or shape of the treated breast as compared to the opposite breast or the original appearance of the treated breast. There may be some mild reddening or darkening of the breast. The thickening or scar tissue within the breast causes only a mild change in the shape or size.
3	FAIR: obvious differences in the size and shape of the treated breast. This change involves a quarter or less of the breast. There can be moderate thickening or scar tissue of the skin and the breast, and there may be obvious color changes.
4	POOR: marked change in the appearance of the treated breast involving more than a quarter of the breast tissue. The skin changes may be obvious and detract from the appearance of the breast. Severe scarring and thickening of the breast, which clearly alters the appearance of the breast, may be found.

My satisfaction about the treatment and results is: (Select the phrase that best describes your satisfaction.)

☐ Totally satisfied
 ☐ Somewhat satisfied
 ☐ Neither satisfied nor dissatisfied
 ☐ Somewhat dissatisfied
 ☐ Totally dissatisfied

Patient
Study ID

--	--	--	--	--	--	--	--	--	--

Before any treatment to your breast, the size of your breasts was: (Select the phrase that best describes your breast size prior to treatment.)

☐
Larger
on left

☐
The same on
both sides

☐
Larger
on right

The size of your breasts now is: (Select the phrase that best describes your breast size now.)

☐
Larger
on left

☐
The same on
both sides

☐
Larger
on right

Thank you for completing this questionnaire!

21 Appendix - Quality of Life questionnaire used for follow-up visits

Form QLF(01-25-2005)

Quality of Life Questionnaire - Follow-up

Page 1 of 6

Patient Initials ,
Last First Middle

Patient Study ID

For patients who receive both radiation and chemotherapy, this should be completed at day 45-60 following start of radiation and at 2-year follow-up.

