3	FAIR: obvious differences in the size and shape of the treated breast. This change involves a quarter or less of the breast. There can be moderate thickening or scar tissue of the skin and the breast, and there may be obvious color changes.
4	POOR: marked change in the appearance of the treated breast involving more than a quarter of the breast tissue. The skin changes may be obvious and detract from the appearance of the breast. Severe scarring and thickening of the breast, which clearly alters the appearance of the breast, may be found.

assessment time point ☐ last week RT ☐ day 45-60 ☐ 2 years

SCL and RTOG PQ

Patient Study ID

--	--	--	--	--	--	--	--	--	--

My satisfaction about the treatment and results is: (Select the phrase that best describes your satisfaction.)

☐ Totally satisfied ☐ Somewhat satisfied ☐ Neither satisfied nor dissatisfied ☐ Somewhat dissatisfied ☐ Totally dissatisfied

Before any treatment to your breast, the size of your breasts was: (Select the phrase that best describes your breast size prior to treatment.)

☐ Larger on left ☐ The same on both sides ☐ Larger on right

The size of your breasts now is: (Select the phrase that best describes your breast size now.)

☐ Larger on left ☐ The same on both sides ☐ Larger on right

Thank you for completing this questionnaire!

assessment time point ☐ last week RT ☐ day 45-60 ☐ 2 years

RT09 PQ

22 Appendix - Form for missing Quality of Life information

Form QMD (01-25-2005)

Page 1 of 1

Missing Data Form for Quality of Life Questionnaire

Submit this form whenever a protocol-scheduled Quality of Life (QOL) Questionnaire (i.e., Form QLT, QLP, or QLF) is not filled out by the patient and the assessment cannot be obtained by phone or mail. No missing data form is required for partially completed QOL forms or patients who have died or had a documented breast cancer recurrence or a second primary cancer.

Patient Initials , <small style="display: block; text-align: center;">Last First Middle</small>	Patient ID
Institution Name / Affiliate Name _____ / _____	
Person Completing Form _____	
Today's Date <small style="display: block; text-align: center;">Month Day Year</small>	
 Last Name First Name Phone 

Are data amended? (check box if yes, and circle amended items)  Yes	

Time Point for this Form (mark one)	

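### BCTOS, the only instrument assigned to the cosmesis endpoint, scores the treated breast against an untreated one, which bilateral patients do not have; including them dilutes the arm comparison

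*Combined protocol and SAP*

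**What the plan says.** Section 4 admits women with disease in both breasts: "If bilateral, pT1-2 breast cancer excised with negative margins AND/OR pTis excised with negative margins". It also admits "Women with previous contralateral breast cancer", with no limit on how the other breast was treated. The only related exclusion is earlier radiation to the ipsilateral breast. The note to Table 2 in Section 5.1 adds: "Patients with bilateral breast cancer will be randomized to receive the same dose and fractionation to both breasts".

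The Protocol Summary, Section 6 and Section 8.1 all name BCTOS self-report as the measure of cosmesis, at baseline, end of radiotherapy, 1 month and 2 years. No other instrument is assigned to that endpoint. On the baseline form (Appendix 3.1) and on the follow-up form, the 22 BCTOS items stand under one heading, "Difference between treated and untreated breast and area", with four response levels from none to large.

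Both forms also carry a four-level appearance rating, Excellent to Poor. Its top grade is defined "when compared to the untreated breast or the original appearance of the breast".

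Section 11 describes analyses for toxicity, fibrosis or telangiectasia, and local recurrence. It gives no test, margin or analysis set for cosmesis.

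**The concern.** A score defined as a difference between two breasts needs one breast that the treatment leaves alone. A bilateral patient has none. If both breasts shrink or harden to a similar degree, the answers that follow the form are at or near no difference, however marked the change.

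Cosmesis is in the trial's title and in its non-inferiority hypothesis. Patients whose score cannot show the treatment effect move both arms towards the same value. In a superiority trial that costs power. In a non-inferiority reading it helps the claim.

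No scoring rule, per-breast rating, exclusion or sensitivity analysis covers these women. The follow-up form does say that a woman with a second primary cancer after entry is not expected to complete further questionnaires, but no rule covers women who enter with two affected breasts. A woman with previous contralateral cancer has a reference breast, but one that earlier treatment may have changed.

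**Working it through.** The plan states no cosmesis figure (no margin, standard deviation, effect size or power), so there is nothing to reproduce. The check has two parts: how the score behaves, and how much dilution could follow.

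**How the score behaves.** Let *i* be the alteration in the index breast and *c* the alteration in the other breast. A BCTOS breast item records roughly D = |i − c|.

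- *Unilateral disease, other breast never treated.* c = 0, so D = i. The item measures what is intended.
- *Bilateral disease.* Both breasts get the same regimen (Table 2), so *c* moves with *i*. If i = c, then D = 0 at every visit, and the change from baseline is also 0. Subtracting baseline removes a starting asymmetry; it does not recover change that the two breasts share.
- *Previous contralateral cancer.* The other breast is not irradiated in the trial, so *c* is roughly fixed at some c0. If c0 > 0 and i is near 0, D is about c0, and the score shows a difference that the index breast did not cause. If *i* then rises but stays below c0, D falls, and worsening reads as improvement. If *i* already exceeds c0 at baseline, the change in D equals the change in *i*, and subtracting baseline works. The direction of error is therefore not fixed, and change from baseline is a partial remedy.

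**How much dilution.** Let *f* be the share of women who contribute no contrast between arms. Then

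observed difference = (1 − f) × true difference + f × 0 = (1 − f) × true difference.

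The documents do not give *f*; the values below are assumptions. Counts are f × 400. The power column is an illustration for an assumed true difference of 0.3 SD, 200 women per arm, full questionnaire completion and a two-sided 5% test:

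power = Φ(0.3 × (1 − f) / √(2/200) − 1.96), where √(2/200) = 0.1.

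| f (assumed) | women of 400 | difference retained | power |
|---|---|---|---|
| 0 | 0 | 100% | Φ(3.00 − 1.96) = 85.1% |
| 2% | 8 | 98% | Φ(2.94 − 1.96) = 83.6% |
| 5% | 20 | 95% | Φ(2.85 − 1.96) = 81.3% |
| 10% | 40 | 90% | Φ(2.70 − 1.96) = 77.0% |
| 20% | 80 | 80% | Φ(2.40 − 1.96) = 67.0% |

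The model suits bilateral patients whose breasts change alike. It does not describe women with previous contralateral cancer, whose error can have either sign. With no cosmesis margin in Section 11, the effect cannot be expressed as a false non-inferiority rate.

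**The case against.** Several points on the other side are fair.

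- *BCTOS is not the only cosmesis information collected.* A reader might infer that nothing else records appearance. That is wrong. The four-level rating (on the follow-up form it sits on a page labelled "SCL and RTOG PQ") allows the breast's own original appearance as reference. The forms also ask about breast size before treatment and now, and about hardening and skin thickening. Nurses score fibrosis with LENT/SOMA, whose table also covers retraction and atrophy. This stands, but the plan assigns none of these to the cosmesis endpoint, so they make the remedy easy without removing the gap.
- *Harm is not shown to be hidden in every such woman.* A reader might extend the masking argument to women with previous contralateral cancer. The documents do not support that: their other breast receives no trial radiation, a baseline BCTOS is planned, and the error can go either way.
- *Zero signal in bilateral women is not proven.* The same dose and fractionation need not produce the same change. Each boost goes to its own tumor bed, and one side may be invasive and the other in situ. Asymmetric change can still register. Attenuation is what can be claimed.
- *The numbers may be small.* The criterion on previous contralateral cancer came in with version 6.0 (07OCT2024), almost five years after version 1.0, which suggests, without proving, that few women will enter under it. That says nothing about bilateral patients.
- *The amendment rationale.* Version 6.0 says that "A history of contralateral breast cancer does not compromise the radiotherapy treatment plan or the outcomes being assessed in this study". A reader might want this corrected. It concerns contralateral history, not bilateral disease, and it belongs to a change log. The operative text is what needs the rule.
- *The larger gap is the absence of any cosmesis analysis in Section 11.* True, but a generic analysis added there would carry this problem with it unless the analysis set is defined.

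**Conclusion.** The point holds in a limited form. For bilateral women the reference that BCTOS requires does not exist. Their scores tend to miss symmetric change, baseline adjustment does not restore it, and including them biases the arm comparison towards no difference. For women with previous contralateral cancer the score is potentially distorted, in an unknown direction, with partial protection from the baseline measurement.

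The size rests on an assumed share: at 2–10% contributing no contrast, 2–10% of a true difference is lost. That is modest, and it would become material only near 10–20%. Several of the 22 items concern the arm and shoulder rather than appearance, so the argument bears mainly on the breast items.

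Cosmesis is a secondary endpoint. A reader might infer that the trial's main conclusion is at risk; it is not, because acute toxicity is graded by CTCAE and does not use BCTOS. Nurse-scored fibrosis is not affected either.

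**What to change.** In Sections 8.1 and 11:

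1. Exclude women with bilateral disease from the main BCTOS cosmesis comparison, using laterality recorded at baseline, so that the analysis set does not depend on anything after randomization.
2. Analyse women with previous contralateral cancer as change from baseline BCTOS, with a sensitivity analysis that leaves them out.
3. Show the all-patient BCTOS result as a sensitivity analysis, and report the number of women in each group by arm.
4. For bilateral women, report the Excellent/Good/Fair/Poor item descriptively, rated against original appearance and stating which breast is rated. The item as printed asks for a single rating and also offers the other breast as a reference, so the instruction has to be explicit. For forms already returned, say where the rated breast is not known.

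The cost is wording plus one instruction for bilateral women, and a small loss of patients from a secondary comparison. The item is already on both forms. No stratification is planned, so the groups may differ slightly in number between arms; the counts in step 3 will show this. Two-year forms from women admitted under the version 6.0 criterion fall due no earlier than about late 2026, so a rule written before then would precede those data. The amendment log needs no change.
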